4.1.4 Radiation Therapy Quality Assurance

[name] or [name] will perform a RT Quality Assurance Review after complete data for the first 20 cases enrolled has been received at the University of Texas Southwestern. [name] or [name] will perform the final review after complete data for the subsequent 15 cases enrolled at the University of Texas Southwestern. These cases will be reviewed within 3 months after this study has reached the target accrual or as soon as complete data for all cases enrolled has been received, whichever occurs first.

4.2 Nivolumab

4.2.1 Treatment Dosage and Administration

Nivolumab administered per standard of care according to institutional guidelines at the discretion of the treating medical oncologist. The standard FDA approved administration and indications of Nivolumab is listed in the FDA website: www.fda.gov or Package Insert https://www.accessdata.fda.gov/drugsatfda_docs/label/2018/125554s058lbl.pdf. Nivolumab may be administered in a community practice setting as long as the treating study oncologist assumes responsibility for all reporting and follow-up requirements.

If Nivolumab dosing is delayed for a drug-related adverse event, treatment may resume when the event has resolved to Grade 1 or baseline. If treatment is delayed > 6 weeks, the subject must be permanently discontinued from study therapy, except in cases where the delay is due to the need for a prolonged steroid taper to manage drug-related adverse events or the delay is not drug related.

4.2.1.1 Toxicities and Dosing Delays/Dose Modifications

Any subject who receives treatment on this protocol will be evaluable for toxicity. Each patient will be assessed for the development of toxicity according to the Time and Events table (5.4). Toxicity will be assessed according to the NCI Common Toxicity Criteria for Adverse Events (CTCAE), version 4.0. No dose modifications for Nivolumab will be allowed. Treatment with Nivolumab will be modified by withholding doses rather than continuing therapy at a reduced dose. We recommend to follow the FDA institutional guidelines or at the discretion of the treating medical oncologist for any dose delay criteria, criteria to resume treatment with Nivolumab and/or discontinuation for nivolumab.

Treatment of Nivolumab Related Infusion Reactions

Since Nivolumab contains only human immunoglobulin protein sequences, it is unlikely to be immunogenic and induce infusion or hypersensitivity reactions. However, if such a reaction were to occur, it might manifest with fever, chills, rigors, headache, rash, pruritus, arthralgias, hypo- or hypertension, bronchospasm, or other symptoms. All Grade 3 or 4 infusion reactions should be reported within 24 hours as an SAE if criteria are met. Infusion reactions should be graded according to NCI CTCAE (version 4.0) guidelines.

Treatment recommendations are provided below and may be modified based on local treatment standards and guidelines, as appropriate:

For Grade 1 symptoms: (Mild reaction; infusion interruption not indicated; intervention not indicated) Remain at bedside and monitor subject until recovery from symptoms. The following prophylactic premedications are recommended for future infusions: diphenhydramine 50 mg (or equivalent) and/or paracetamol 325 to 1000 mg (acetaminophen) at least 30 minutes before additional Nivolumab administrations.

For Grade 2 symptoms: (Moderate reaction requires therapy or infusion interruption but responds promptly to symptomatic treatment [eg, antihistamines, non-steroidal anti-inflammatory drugs, narcotics, corticosteroids, bronchodilators, IV fluids]; prophylactic medications indicated for ≤24 hours) Stop the Nivolumab infusion, begin an IV infusion of normal saline, and treat the subject with diphenhydramine 50 mg IV (or equivalent) and/or paracetamol 325 to 1000 mg (acetaminophen); remain at bedside and monitor subject until resolution of symptoms. Corticosteroid or bronchodilator therapy may also be administered as appropriate. If the infusion is interrupted, then restart the infusion at 50% of the original infusion rate when symptoms resolve; if no further complications ensue after 30 minutes, the rate may be increased to 100% of the original infusion rate. Monitor subject closely. If symptoms recur then no further Nivolumab will be administered

at that visit. Administer diphenhydramine 50 mg IV, and remain at bedside and monitor the subject until resolution of symptoms. The amount of study drug infused must be recorded on the case report form (CRF). The following prophylactic premedications are recommended for future infusions: diphenhydramine 50 mg (or equivalent) and/or paracetamol 325 to 1000 mg (acetaminophen) should be administered at least 30 minutes before additional Nivolumab administrations. If necessary, corticosteroids (recommended dose: up to 25 mg of IV hydrocortisone or equivalent) may be used.

For Grade 3 or Grade 4 symptoms: (Severe reaction, Grade 3: prolonged [ie, not rapidly responsive to symptomatic medication and/or brief interruption of infusion]; recurrence of symptoms following initial improvement; hospitalization indicated for other clinical sequelae [eg, renal impairment, pulmonary infiltrates], Grade 4: life-threatening; pressor or ventilator support indicated) Immediately discontinue infusion of Nivolumab. Begin an IV infusion of normal saline, and treat the subject as follows: Recommend bronchodilators, epinephrine 0.2 to 1 mg of a 1:1,000 solution for subcutaneous administration or 0.1 to 0.25 mg of a 1:10,000 solution injected slowly for IV administration, and/or diphenhydramine 50 mg IV with methylprednisolone 100 mg IV (or equivalent), as needed. Subject should be monitored until the investigator is comfortable that the symptoms will not recur. Nivolumab will be permanently discontinued. Investigators should follow their institutional guidelines for the treatment of anaphylaxis. Remain at bedside and monitor subject until recovery from symptoms. In the case of late-occurring hypersensitivity symptoms (eg, appearance of a localized or generalized pruritus within 1 week after treatment), symptomatic treatment may be given (eg, oral antihistamine or corticosteroids).

Continued Treatment Beyond Progression of Disease

As indicated above, we will use the RECIST and ir-RECIST criteria for tumor measurement and RR determination. Accordingly, an initial progression on the first set of scans should be verified by a second set of scans before considering it as disease progression and before the decision to discontinue treatment is made. If progression is confirmed on the second set of scans, the first date will be used in evaluations of PFS. (Scans are collected at the time points listed in the study procedures)

In addition, accumulating evidence indicates a minority of subjects treated with immunotherapy may derive clinical benefit from continued treatment despite initial evidence of progressive disease. For this reason, subjects will be permitted to continue study therapy beyond initial investigator-assessed ir-RECIST) progression as long as they meet the 2 criteria listed below at the discretion of the treating medical oncologist:

- Investigator-assessed clinical benefit,
- and
- Subject is tolerating study drug.

Subjects should discontinue study therapy upon evidence of further progression at the discretion of the treating medical oncologist, defined as an additional 10% or greater increase in tumor burden from time of initial progression (including all target lesions and new measurable lesions).

New lesions are considered measurable at the time of initial progression if the longest diameter is at least 10 mm (except for pathological lymph nodes, which must have a short axis of at least 15 mm). Any new lesion considered non-measurable at the time of initial progression may become measurable and therefore included in the tumor burden measurement if the longest diameter increases to at least 10 mm (except for pathological lymph nodes, which must have an increase in short axis to at least 15 mm). For statistical analyses that include the investigator-assessed progression date, subjects who continue treatment beyond initial investigator-assessed, ir-RECIST 1.1-defined progression will be

considered to have investigator-assessed progressive disease at the time of the initial progression event.

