Treatment with immunotherapies has been reported to cause a “tumor flare” which denotes the apparent radiographic increase in tumor burden or occurrence of new lesions before a true clinical response can be established. This “flare” is thought to be due to a transient increase in immune cell infiltration while the immune system is being primed. Therefore, RECIST criteria may fail to accurately report RR and some patients will be taken off therapy before a true response is measured. In the CheckMate 025 trial, 44% of patients who progressed per RECIST criteria were continued on Nivolumab if they were thought to have clinical benefit. In addition, in the phase II trial of Nivolumab dose escalation trial, treatment beyond first RECIST-criteria progression was allowed in patients who tolerated Nivolumab and exhibited investigator-assessed clinical benefit. 17%, 22% and 26% of patients in the 0.3, 2 and 10 mg/kg groups were treated beyond progression. Median number of doses received after RECIST progression was 4.5, 7.5 and 8.5 in the 0.3, 2 and 10 mg/kg groups. Median PFS was 2.7 mos, 4.0 mos and 4.2 mos in the 0.3, 2 and 10 mg/kg groups using the RECIST criteria but increased to 4.3, 5.4 and 6.9 mos respectively using immune-response PFS. In a subgroup analysis, 69% (25/36) of patients who received treatment beyond first progression, defined as patients receiving their last Nivolumab dose >6 weeks after RECIST-defined progression, demonstrated sustained reductions in tumor burden or lesion stabilization with an acceptable safety profile. Median OS for patients treated beyond first progression was 22 mos vs 12 mos for those not treated. Thus, patients will be allowed to stay on Nivolumab after their first RECIST-criteria progression per the treating physician. Data will be evaluated using the RECIST criteria for primary endpoint and ir-RECIST for secondary endpoint.

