6.0 Measurement of Effect

6.1 Antitumor Effect

Response and progression will be evaluated in this study using the new international criteria proposed by the Response Evaluation Criteria in Solid Tumors (RECIST) Committee [JNCI 92(3):205-216, 2000]. The only change from RECIST v.1.1 being implemented in this study is a confirmation of new lesions or progressive disease (PD) by a second scan >6 weeks apart, based on the immune RECIST (ir-RECIST) criteria proposed by Wolchok. *et. al* that is appropriate for immune-related treatment response [89]. This is primarily because immune response often can take longer time as compared to chemotherapy before producing a radiographic response and during this time new lesions may arise which will eventually regress. If it were not for a second confirmation, these patients would be labeled to have failed therapy. Additional criteria for bone lesions and clinical endpoints of pathologic fracture and cord compression are added to this study (see Section 6.1.4). Changes in only the largest diameter (unidimensional measurement) of the tumor lesions are used in the RECIST v1.1 criteria outlined in <http://www.recist.com/>. The primary endpoint will be evaluated using RECIST v1.1 and secondary endpoint will be ir-RECIST.

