6.1.4 Response Criteria

6.1.4.1 Evaluation of Target Lesions

Complete Response (CR): Disappearance of all target lesions, determined by two separate observations conducted no less than 4 weeks apart. Any pathological lymph nodes must have reduction in short axis to < 10 mm. There can be no appearance of new lesions.

Partial Response (PR): At least a 30% decrease in the sum of the longest diameter (LD) of target lesions, taking as reference the baseline sum LD. There can be no appearance of new lesions.

Progressive Disease (PD): At least a 20% increase in the sum of the LD of target lesions, taking as reference the smallest sum LD recorded since the treatment started, or the appearance of one or more new lesions verified by a second scan > 6 weeks apart. In addition to the relative increase of 20%, the sum must also demonstrate an absolute increase of at least 5 mm.

Stable Disease (SD): Neither sufficient shrinkage to qualify for PR nor sufficient increase to qualify for PD, taking as reference the smallest sum LD since the treatment started.

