6.1.4.3 Evaluation of Best Overall Response

The best overall response is the best response recorded from the start of the treatment until disease progression/recurrence (taking as reference for progressive disease the smallest measurements recorded since the treatment started). The subjects' best response assignment will depend on the achievement of both measurement and confirmation criteria.

Target Lesions	Non-Target Lesions	New Lesions	Overall Response	Best Response for this Category Also Requires:
CR	CR	No	CR	≥4 wks. confirmation
CR	Non-CR/Non-PD	No	PR	≥4 wks. confirmation
PR	Non-PD	No	PR	
SD	Non-PD	No	SD	Documented at least once ≥4 wks. from baseline
PD	Any	Yes or No	PD	no prior SD, PR or CR
Any	PD*	Yes or No	PD	
Any	Any	Yes	PD	

* In exceptional circumstances, unequivocal progression in non-target lesions may be accepted as disease progression.
 
Note: Subjects with a global deterioration of health status requiring discontinuation of treatment without objective evidence of disease progression at that time should be reported as “symptomatic deterioration”. Every effort should be made to document the objective progression even after discontinuation of treatment.
				

Note: If subjects respond to treatment and are able to have their disease resected, the patient’s response will be assessed prior to the surgery.

6.1.4.4 Evaluation of Bone Lesions:

Bone lesions will be evaluated either by CT or MRI, whichever is deemed to be better suited by baseline studies. Since the size of the lesion is difficult to measure in a bone scan, particularly if it is not well visible in CT, the following guideline will be used. Any ambiguity will require MRI for resolution:

6.1.4.4.1 Progression of bone lesions will be defined as follows:

- Appearance of 1 or more new bone lesion in CT scan, confirmed by a repeat scan in ≥6 weeks.

6.1.4.4.2 Response of bone lesions in CT scan will be defined by either a complete resolution (CR) at the metastatic sites or partial resolution (PR) of radiotracer uptake by a radiologist.

6.1.4.5 Evaluation of Pathologic Fracture:

Any clinical suspicion of pathologic fracture will prompt radiologic evaluation with plain film, CT or MRI as appropriate and if confirmed by a radiologist, will constitute progression, unless it is at a treated site, in which case a treatment-related toxicity will be considered. In that case, patients will be referred for orthopedics specialist evaluation.

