11.2 Sample Size and Accrual

The first six patients assigned will be assessed for feasibility, safety, and toxicity for interim safety of the trial 8 weeks post-registration. If more than 3 patients experience \geq Grade 3 SAE attributed to the SAbR+Nivolumab out of 6 patients, the study will be held until approval from DSMC.

The previous studies show that the maximum RR for mRCC patients treated with Nivolumab is 25%. We expect that the addition of SAbR to Nivolumab will increase the RR to 50% i.e. a 100% increase compared to the historical RR to Nivolumab alone. In our current ongoing phase II clinical trial (STU 012013-041) with similar patient population and treatment strategy of SABR + immunotherapy using IL-2, we are noticing a 53% RR with the combination whereas the historically reported response rate of IL-2 alone treatment is 20% (1). Therefore, we have increased the RR by $>150\%$. Therefore, in oncology clinical trials, it is not uncommon to see such increases since the baseline RR is often low.

The calculation of the sample size is based on the RR. In this phase II trial, we will recruit a total of 19 patients including the 6 patients that will be used for interim safety analysis. A total sample size of 19 achieves 80% power to detect 25% absolute difference in RR (25% vs. 50%) using an exact binomial test at a 0.2 two-sided significance level. To allow for potential subject dropouts, the accrual goal will be increased by an additional 2 patients for a total of 21 patients. The sample size was estimated using a sample size software PASS 14 ("Hintze, J. (2015). PASS 14. NCSS, LLC. Kaysville, Utah, USA. www.ncss.com.")

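### The primary response rate is labelled RECIST v1.1, but study-wide second-scan wording leaves open counting a response that follows a first, unverified progression

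*Combined protocol and SAP*

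**What the plan says.** **The label.** Section 6.1 states: "The primary endpoint will be evaluated using RECIST v1.1 and secondary endpoint will be ir-RECIST". Section 2.1 makes the same split, and 2.2.1 lists the ir-RECIST response rate as a separate secondary objective.

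**The progression rule.** Section 6.1 also describes second-scan confirmation of new lesions or progression as the one departure from RECIST v1.1 that the study adopts. Section 2.4.3 defines progression only by ir-RECIST with a verifying scan. Section 4.2.1.1 (Continued Treatment Beyond Progression of Disease) names RECIST and ir-RECIST together for measuring tumours and determining response rate. It then draws the consequence that "an initial progression on the first set of scans should be verified by a second set of scans before considering it as disease progression".

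**The response criteria.** Section 6.1.4 contains a single set. In 6.1.4.1, progression of target lesions is a 20% increase (and at least 5 mm) "or the appearance of one or more new lesions verified by a second scan > 6 weeks apart". In 6.1.4.3, "The best overall response is the best response recorded from the start of the treatment until disease progression/recurrence".

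**Treatment after progression.** Section 2.1 says: "Thus, patients will be allowed to stay on Nivolumab after their first RECIST-criteria progression per the treating physician".

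**The test.** Sections 11.2 and 11.3 compare the response rate with a historical 25% "using an exact binomial test at a 0.2 two-sided significance level", with 19 patients and a target of 50%.

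**The concern.** A RECIST v1.1 response rate and an ir-RECIST response rate should differ in exactly one group: patients who respond after an initial progression. The plan names both endpoints but writes one rule set. Its general progression rule says a first progression does not count until a second scan verifies it. If it does not count, the best-response window in 6.1.4.3 has not closed. Because patients may stay on nivolumab and continue to be scanned, later shrinkage can be recorded as a response.

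Two competent analysts could thus report different primary results from the same scans, each citing the protocol. If the more permissive reading were used, the observed rate would rise through the scoring rule rather than through SABR, and would be tested against a comparator that may not have been scored that way. The issue concerns the primary response rate, not PFS.

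**Working it through.** **1. Which route is open?** Take a patient whose first follow-up scan meets the RECIST 1.1 threshold for progression, whose next scan does not confirm it, and who later meets the partial-response threshold (a 30% decrease from baseline).

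| First event | Text that makes it progression | Text that says it is not yet progression |
|---|---|---|
| Target lesions up by 20% or more | RECIST v1.1 label (2.1, 6.1); 6.1.4.1, if the second-scan phrase attaches only to new lesions, as its position suggests; table in 6.1.4.3 | 4.2.1.1 and 6.1 (second scan for progression in general); 2.4.3 |
| New lesion | RECIST v1.1 label; 6.1.4.2; table in 6.1.4.3 (any new lesion is progression); CR and PR in 6.1.4.1 exclude new lesions | 4.2.1.1, 6.1, 2.4.3, and the second-scan phrase in 6.1.4.1 |

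The first row is the clearer route: once the target lesions shrink, nothing in the definition of partial response blocks it. The second row is an outright contradiction, because 6.1.4.1 to 6.1.4.3 bar a response with a new lesion while other sentences say an unverified new lesion is not yet progression.

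**2. Does the dating rule close the gap?** Section 4.2.1.1 places progression at the initial event for patients treated on. That rule covers analyses that use a progression date, and progression defined by ir-RECIST. The same section carries the first date back for PFS only when progression is confirmed. Neither provision covers a first RECIST 1.1 progression that is never confirmed.

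**3. Reproducing the design.** Inputs from 11.2: p0 = 0.25, p1 = 0.50, two-sided alpha 0.2 (0.10 per tail), exact binomial test. Formula:

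P(X ≥ r | n, p) = Σ from k = r to n of C(n,k) p^k (1 − p)^(n − k)

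At n = 19 the test rejects high at 8 or more responders (upper tail 0.0775) or low at 1 or fewer (lower tail 0.0310). The total is 0.0775 + 0.0310 = 0.1085. Power at 50% is 0.8204. No n from 8 to 18 reaches 80% (n = 18 gives 0.7597), so the planned 19 is reproduced.

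**4. Effect of one patient.** Each patient is 1/19 = 5.3 points.

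- 7/19 (36.8%): upper tail 0.175; doubled p = 0.350; not significant.
- 8/19 (42.1%): upper tail 0.0775; doubled p = 0.155; significant at two-sided 0.2.

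**5. Effect on the false-positive chance.** Let q be the points added to a true RECIST rate of 25% by responses after a first progression. The documents give no value, so q is an assumption with a range of 0 to 10 points.

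| q (points) | Expected such patients, 19 × q/100 | P(X ≥ 8), n = 19 | P(X ≥ 9), n = 21 |
|---|---|---|---|
| 0 | 0 | 0.077 | 0.056 |
| 2 | 0.38 | 0.113 | 0.086 |
| 5 | 0.95 | 0.182 | 0.148 |
| 10 | 1.9 | 0.334 | 0.294 |

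The last column covers analysis of all 21 accrued, where the upper critical value is 9. The nominal 0.10 upper tail is exceeded from about 2 points with 19 analysed and about 3 points with 21 (0.104).

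**The case against.** The strongest reply is that the primary criterion is named twice, in 2.1 and 6.1. Section 2.1 discusses tumour flare, accepts that RECIST may miss such responses, and keeps RECIST as primary anyway. An analyst who follows the named criterion would exclude them. Section 4.2.1.1 appears under a treatment-continuation heading, and its explicit consequences are when to stop treatment and which date to use for PFS. For progression that is confirmed, its initial-event rule read with 6.1.4.3 would probably exclude later responses.

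Most of this stands, and it rules out three stronger readings:

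- A reader might infer that the plan intends to score the primary endpoint by immune-modified rules, or that the primary and secondary response rates are identical. The explicit split in 2.1, 2.2.1 and 6.1 does not support that. This is an unresolved conflict, not a stated intent.
- A reader might infer that a patient with a new lesion on the first scan and later shrinkage is plainly a responder under 6.1.4. The response definitions and the best-response table say otherwise; on that case the text contradicts itself.
- A reader might take the 44% in 2.1 as a sign of large bias. It is the share of progressing patients in the cited phase 3 trial who continued nivolumab, not a response rate. The 69% (25 of 36) in the same section mixes tumour reduction with stabilisation.

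What the reply does not remove is that 4.2.1.1 ties the second-scan rule to response-rate determination under both criteria, 6.1 describes it as the study's one change, and no sentence closes primary best response at the first RECIST 1.1 progression.

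**Conclusion.** The point holds as an ambiguity in the definition of the primary endpoint. A response after a first, unverified RECIST 1.1 progression can be counted or excluded depending on the section followed, most clearly when target-lesion growth is not confirmed and then reverses. At the decision boundary one such patient changes the conclusion.

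The size of any bias is unknown. The false-positive figures (7.7% rising to 11.3%, 18.2% or 33.4% for 2, 5 or 10 added points) rest on an assumed q. They also assume that the 25% comparator was scored by unmodified RECIST, which the documents do not say. The sample size itself is sound. The wording should be settled before response data are read; the conflict does not invalidate the design.

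**What to change.** In 6.1.4.3 and 11.3, state that for the primary response rate:

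- best overall response uses only assessments up to the first RECIST 1.1 progression (target-lesion growth, non-target progression or a new lesion), without second-scan verification;
- a patient whose first event is progression is a non-responder, whether or not treatment continues;
- later responses count only in the ir-RECIST response rate (2.2.1).

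Confine the verification wording in 2.4.3, 4.2.1.1, 6.1 and 6.1.4.1 to the ir-RECIST endpoints. Leave the treatment-continuation rules as they are.

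The cost is wording only: the same scans, readers and 19 evaluable patients, with the critical value still 8. The primary rate may come out slightly lower. If the 50% target was meant to include post-progression responses, which the plan does not say, the power of the strict endpoint would fall from 82.0% to 77.1% with 2 such points, or to 68.3% with 5. Section 11.2 should therefore also say which criterion the 50% refers to.
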